#### **8.5.3 Six-minute walk test (6MWT)**

The 6-minute walk test (6MWT) is a simple, economical and reproducible test that measures how many meters a person can walk in 6 minutes. Repeated measurement of the 6MWT over time has been used in studying numerous musculoskeletal, pulmonary, and cardiovascular conditions and is a validated outcome in investigational drug trials.

Patients will be instructed by the test administrator using a script and established testing protocol. The testing should be conducted on an individual basis (patient and testers) with no additional audience or support other than that of the trained personnel conducting the test. If a walking aid is required at baseline, patients will be asked to use the least assistive walking aid that in their opinion will enable them to complete the 6MWT safely. Patients should be encouraged to use the same walking aid when performing all tests throughout the study.

A change in walking aid to perform the test is permitted if required for safety reasons (e.g., deterioration of balance). The testing should occur at approximately the same time of the day as the baseline assessment to prevent any possible diurnal variations. The same test administrator should perform all repeat tests on a patient whenever possible to reduce technician-related differences in test performance.

In circumstances where the test is interrupted for reasons other than patient fatigue the test may be repeated once, preferably on the same day (with a minimum 60 minute rest period). If re-testing on the same day is not possible, the test may be repeated as soon as possible, but within 2-3 days of the original attempt.

Patients resting values of oxygen saturation (%), heart rate (bpm), and Borg Questionnaire score will be recorded before the test. Oxygen saturation (%), heart rate (bpm), distance walked (meters), and Borg Questionnaire score will be recorded at the end of the 6MWT. Requirement of rescue medications, including supplemental oxygen therapy, and any adverse events occurring during the 6MWT will be recorded. If a patient is on chronic oxygen therapy,

supplemental oxygen will be allowed during the 6MWT; however, the same level/rate of supplemental oxygen should be maintained through the initial 6MWT and all subsequent trials. Complete details of course set-up, test administration, equipment and recording into the eCRF are described in the Site Operations Manual.

#### **8.5.4 Serum IL-1 $\beta$**

Corporate Confidential Information

#### **8.5.5 Pulmonary function testing**

For details on pulmonary function testing please refer to below sections and the Biomedical Systems Centralized Spirometry, DLco and Lung Volumes Procedure Manual.

##### **8.5.5.1 Diffusing Capacity (DLco)**

Diffusion capacity for carbon monoxide (DLco) will be determined according to ATS guidelines ([MacIntyre et al 2005](#)). Measurements will include DLco and alveolar volume (VA). DLco is determined by measuring the uptake of carbon monoxide from the lung over a breath-holding period. VA represents an estimate of lung gas volume into which CO is distributed and then transferred across the alveolar capillary membrane making it critical in the measurement of DLco. VA is typically measured simultaneously with CO uptake by calculating the dilution of an inert tracer gas (e.g., argon, methane, or helium). In normal subjects, the sum of VA and VD (dead space volume) closely matches the total lung capacity (TLC) determined by plethysmography. However, in cases of poor gas mixing in patients with obstructed airways, tracer gas dilution is markedly reduced leading to VA values that are significantly less than those expected based on actual total thoracic gas volumes. Additional information for obtaining DLco is provided in the Pulmonary Function Tests Manual.

##### **8.5.5.2 Lung Volumes**

A body plethysmograph will be used to measure Functional Residual Capacity (FRC), Inspiratory Capacity (IC), Total Lung Capacity (TLC), and Residual Volume (RV). All plethysmography evaluations should follow the recommendations of the ATS/ERS Task force: Standardization of the measurement of lung volumes ([Wanger et al 2005](#)). Additional information for conduct of plethysmography will be provided in the Biomedical Systems Centralized Spirometry, DLco and Lung Volumes Procedure Manual.

### **8.5.5.3 Spirometry**

Spirometry testing will be performed according to the American Thoracic Society guidelines ([Miller et al 2005a](#); [Miller et al 2005b](#)) at screening to assess patients' eligibility for the study and as detailed in the assessment schedule. Eligibility criteria are based on FVC in percent of predicted, stratified by gender, age, height, and race ([Pellegrino et al 2005](#)).

The spirometry equipment used during the trial must meet or exceed the minimal ATS/ERS recommendations for diagnostic spirometry equipment as defined in the guidelines ([Miller et al 2005b](#)).

The same spirometry equipment should be used for all assessments performed by a subject. A limited number of staff, as designated by the investigator, will evaluate all patients at all visits throughout the entire trial. Where possible the same technician should perform all maneuvers for an individual subject. All staff conducting the spirometry tests must have received appropriate training, which must be documented.

Results from FVC, FEV1, FEV3 and FEV6 tests are highly dependent on effort and cooperation from the subject. Thus, throughout the maneuver, enthusiastic coaching of the subject is required.

All clinic visits will start in the morning. The following spirometry measurements will be taken: forced vital capacity (FVC); absolute and FVC% (forced vital capacity, expressed as a percentage of the normal expected value) and forced expiratory volume in one second (FEV1). Additional spirometry data to be captured include FEF25-75, FEV1/FVC, FEV3/FVC and FEV6.

For all clinic spirometry assessments, three acceptable maneuvers should be performed for each time-point. All spirometry maneuvers should be performed in sitting position whilst wearing nose clips. The FEV1 and FVC values recorded in the CRF must be the highest values measured irrespective of whether or not they occur on the same curve. All displaceable volumes will be reported in liters (L) at the following conditions: normal body temperature (37° C), ambient pressure, saturated with water vapor (BTPS).

Additional information for conduct of spirometry evaluations is provided in the Biomedical Systems Centralized Spirometry, DLco and Lung Volumes Procedure Manual.

### **8.5.5.4 Spirometry Reversibility Test**

Two spirometry evaluations will be performed at Visit 101 and Visit 107, the first prior to use of salbutamol/albuterol, the second performed after intake of salbutamol/albuterol. The initial spirometry assessment will be performed after a wash-out period of at least 6 hours for a short-acting  $\beta$ -2 agonist and at least 48 hours for a long acting  $\beta$ -2 agonist. After the initial spirometry assessment salbutamol/albuterol is administered, and the second spirometry assessment is performed within 30 min of administration. Investigators should follow the reversibility procedures cited in the ATS/ERS guidelines above with regard to bronchodilator use. The primary spirometry readout will be the post-bronchodilator FVC.

Reversibility (%) will be calculated as follows:

(FEV1 (post bronchodilator) – FEV1 (pre-bronchodilator) x 100)/FEV1 (pre-bronchodilator)

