### 2.2 Secondary objectives

Secondary objectives	Endpoints related to secondary objectives

To determine the effect of ACZ885 on decreasing the maximum standardized uptake value (SUVmax) [F-18]FDG-PET in nodules (nodular uptake regions) after 12 weeks of treatment, compared to placebo.

	

Percent change from initial scan in [F-18]FDG-PET SUVmax at week 12

To determine the effect of ACZ885 versus placebo on other parameters of pulmonary function testing (i.e., absolute FVC, FEV1, FEV1/FVC, FEV3, FEF25-75, FEV3/FVC, FEV6, TLC, RV, RV/TLC, DLco and post-bronchodilator FEV1/reversibility) in patients with sarcoidosis at 24 weeks compared to baseline

	

Lung function testing results at 24 weeks compared to baseline

To determine the effect of ACZ885 versus placebo on HRCT of patients with sarcoidosis at 24 weeks compared to initial HRCT scan as measured by side-by-side comparison by blinded reviewers and HRCT scoring

	

HRCT results at 24 weeks compared to HRCT initial scan measured by blinded reviewers and HRCT scoring

To determine the effect of ACZ885 versus placebo on the 6-minute walk test (6MWT) distance of patients with sarcoidosis at 12 and 24 weeks compared to baseline

	

6MWT results at week 12 and 24 compared to baseline

Secondary objectives	Endpoints related to secondary objectives

• To determine the effect of ACZ885 on additional [F-18]FDG-PET outcomes (i.e., SUVmean, SUVpeak and volume of the lesions) after 12 weeks of treatment compared to placebo

	

• Percent change from initial scan in additional [F-18]FDG PET outcomes at week 12

• To assess the safety and tolerability of ACZ885 in patients with sarcoidosis as measured by adverse events (AEs)

	

• Adverse events in patients taking ACZ885 compared to placebo

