## **6.2 Secondary objectives**

### **6.2.1 Variables**

Secondary variables for this study are:

- [F-18]FDG-PET/CT
- HRCT
- Pulmonary function tests: Change from baseline in absolute and % predicted FVC, FEV1, FEF25-75, FEV1/FVC, FEV3, FEV3/FVC, FEV6, TLC, RV, RV/TLC, DLCO, and post-bronchodilator FEV1/reversibility and other parameters as needed
- 6MWT outcomes: Change from baseline in distance, oxygen saturation, hearth rate and Borg Questionnaire score

For the pulmonary function test parameters the direction of benefit is as follows

- an increase in values is beneficial: absolute and % predicted FVC, FEV1, FEF25-75, FEV1/FVC, FEV3, FEV6, FEV3/FVC, DLCO
- a decrease in values is beneficial: RV, TCL, RV/TCL.

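### The bronchodilator reversibility formula has a misplaced bracket and, taken as written, gives about −99% for every patient

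*Protocol*

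**What the plan says.** Reversibility belongs to a secondary objective. Protocol section 2.2 ends its list of further lung function parameters with "DLco and post-bronchodilator FEV1/reversibility) in patients with sarcoidosis at 24 weeks compared to baseline". The objectives table in SAP section 1.3.2 repeats it, and SAP section 6.2.1 lists "post-bronchodilator FEV1/reversibility and other parameters as needed" among the pulmonary function variables to be taken as change from baseline.

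The derivation is in Protocol section 8.5.5.4. "Two spirometry evaluations will be performed at Visit 101 and Visit 107", one before and one after salbutamol/albuterol. SAP section 6.1.1 identifies the visits with both assessments as Day 1 and Week 24. The section then announces "Reversibility (%) will be calculated as follows", and after an opening outer bracket the expression reads "FEV1 (post bronchodilator) – FEV1 (pre-bronchodilator) x 100)/FEV1 (pre-bronchodilator", followed by a final closing bracket. The part at issue is "FEV1 (pre-bronchodilator) x 100)/FEV1 (pre-bronchodilator".

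The visible SAP text gives no formula for reversibility. The same protocol section refers to ATS/ERS procedures, but only for how the bronchodilator is used.

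**The concern.** A percent change takes the difference first, then scales it by 100 and divides by the starting value. In the printed expression the outer bracket closes after the factor of 100 and not before it. By ordinary precedence the multiplication is done first and applies only to the pre-bronchodilator FEV1. The result is no longer a percent change.

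If reversibility were derived literally from this line, every individual value at Day 1 and Week 24 would be wrong. The listings and summary statistics would be uninterpretable as percentages, and change from baseline would be on the wrong scale. If the programmer quietly corrects the line instead, the analysis departs from the protocol text with no record of it.

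**Working it through.** **Inputs.** The formula and its label are from Protocol section 8.5.5.4. The documents give no FEV1 values and no numerical reversibility result, so there is no stated figure to reproduce. The FEV1 values below are illustrative, and the range of post/pre ratios (0.90 to 1.50) is an assumption.

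**Is it a text-reading artefact?** The printed expression has four opening and four closing brackets. A single bracket lost or added in reading the PDF would leave them unbalanced, so an artefact is unlikely. It cannot be fully excluded without the PDF.

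**Algebra.**

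- As written: (post − pre × 100)/pre = post/pre − 100.
- As intended: (post − pre) × 100/pre = 100 × (post/pre − 1).

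Both depend only on the ratio post/pre and not on the absolute FEV1. Calculations at pre = 1, 2 and 3 L gave identical results.

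**One patient.** Pre 2.0 L, post 2.2 L:

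- As written: (2.2 − 2.0 × 100)/2.0 = −197.8/2.0 = −98.9.
- As intended: (2.2 − 2.0) × 100/2.0 = 20/2.0 = +10.0.

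**Over the assumed range.**

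| post/pre | As written | Intended (%) |
|---|---|---|
| 0.90 | −99.10 | −10 |
| 1.00 | −99.00 | 0 |
| 1.05 | −98.95 | +5 |
| 1.12 | −98.88 | +12 |
| 1.20 | −98.80 | +20 |
| 1.30 | −98.70 | +30 |
| 1.50 | −98.50 | +50 |

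A patient with no response at all would be recorded at −99.

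**Change between visits.** The constant −100 cancels, leaving the Week 24 ratio minus the Day 1 ratio. The intended change is 100 times that difference. A fall in true reversibility from 10% to 5% (ratios 1.10 and 1.05) gives:

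- As written: −98.95 − (−98.90) = −0.05.
- As intended: 5 − 10 = −5 percentage points.

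**Can it be undone?** Yes. Combining the two formulas, intended = 100 × (as written + 99). For the patient above, 100 × (−98.9 + 99) = +10. The error is an exact linear rescaling, so no information is lost, provided that the derived values are not rounded too coarsely.

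**The case against.** The strongest reply is that nobody would carry out the line literally. It is labelled as a percentage and contains the right terms, and no competing definition would produce post/pre − 100. Values near −99 for every patient, responders and non-responders alike, would be caught at the first output check.

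SAP section 1.1 also assigns derived-variable specifications to a separate programming document, and Protocol section 8.5.5.3 refers spirometry detail to a procedure manual. Neither is available here, and either may hold the correct expression.

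The variable also carries little weight. Protocol section 11.5.1.3 only lists and summarises the other pulmonary function tests. SAP section 6.2.3 models FEV1, FEV3 and FEV6 but not reversibility, and reversibility is absent from the direction-of-benefit list in SAP section 6.2.1. The underlying pre- and post-bronchodilator FEV1 values are measured in any case, so a mistake could be repaired.

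All of this stands as an argument about consequence. It means that the statement that no other formula exists applies only to the protocol and the visible SAP text, and that a wrong reported result is possible but not likely. It does not make the printed formula right, and unseen documents cannot be assumed to cure it.

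**Conclusion.** The concern holds: the formula is wrong as written. Taken literally, it returns post/pre − 100, which is between −99.1 and −98.5 for any ratio from 0.90 to 1.50, and it shrinks between-visit changes 100-fold. The algebra needs no assumption beyond ordinary operator precedence. Only the ratio range and the litre values are assumed. The harm is conditional on derivation from the protocol text without correction.

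The point is minor. It concerns one descriptively reported secondary variable, the intent is clear, and the error is reversible. The primary endpoint (change in percent predicted FVC), the sample size and the efficacy criterion do not use this formula.

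**What to change.** In Protocol section 8.5.5.4, close the bracket before the factor of 100:

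Reversibility (%) = 100 × (FEV1 post − FEV1 pre)/FEV1 pre

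Give the same expression in SAP section 6.2.1 where the variable is listed, so that the visible analysis plan has a usable definition. Confirm that the programming specification and the spirometry procedure manual agree with it. If the sponsor prefers to keep derivations only in the programming specification, a cross-reference from the SAP would serve.

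The cost is one bracket moved and one line added. No assessment, visit or sample size changes. Protocol section 13.1 requires a written amendment for any protocol change, so the correction can be carried in the next one, with the SAP line recording the intended formula in the meantime.

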## **8.6 Safety**

Safety assessments are specified below; methods for assessment and recording are specified in the Site Operations Manual, with the [Assessment Schedule](#) detailing when each assessment is to be performed.

### **8.6.1 Physical examination**

See the Site Operations Manual for details.

### **8.6.2 Vital signs**

- Blood pressure (BP)
- Pulse
- Body temperature (same method of measurement should be used throughout study)

### **8.6.3 Height and weight**

- Height
- Body weight

### **8.6.4 Laboratory evaluations**

In the case where a laboratory assessment that is listed in the inclusion/exclusion criteria is outside of a protocol-specified range at screening and/or at the initial baseline, the assessment may be repeated once prior to randomization. If the repeat value remains outside of protocol-specified ranges, the subject is excluded from the study.

In the case where a laboratory range is not specified by the protocol, but is outside the reference range for the laboratory at screening and/or initial baseline, a decision regarding whether the result is of clinical significance or not shall be made by the investigator and shall be based, in part, upon the nature and degree of the observed abnormality. The assessment may be repeated once prior to randomization.

In all cases, the investigator must document in the source documents the clinical considerations (i.e., result was/was not clinically significant and/or medically relevant) in allowing or disallowing the subject to continue in the study.

Clinically relevant deviations of laboratory test results occurring during or at completion of the study must be reported and discussed with Novartis personnel. The results should be evaluated for criteria defining an adverse event and reported as such if the criteria are met. Repeated evaluations are mandatory until normalization of the result(s) or until the change is no longer clinically relevant. In case of doubt, Novartis personnel should again be contacted.

## **Hematology**

Hemoglobin, hematocrit, red blood cell count, white blood cell count with differentials (e.g., neutrophils, basophils, eosinophils, monocytes, lymphocytes) and platelet count will be measured.

## **Clinical chemistry**

Albumin, alkaline phosphatase (ALP), total bilirubin, bicarbonate/CO2, calcium, cholesterol, chloride, creatinine, CK,  $\gamma$ -GT, glucose, LDH, inorganic phosphorus, lipase, amylase, magnesium, potassium, total protein, AST, ALT, sodium, triglycerides, urea/BUN and uric acid.

If the total bilirubin concentration is increased above 1.5 times the upper limit of normal, direct and indirect reacting bilirubin should be differentiated.

## **Urinalysis**

A semi-quantitative "dipstick" evaluation for the following parameters will be performed: specific gravity, pH, glucose, protein, bilirubin, ketones, nitrite, leukocytes and blood.

Microscopy, WBC, RBC and casts will also be assessed in case of an abnormal dipstick test.

### **8.6.5      ECG**

Full details of all procedures relating to the ECG collection and reporting are contained in the Site Operations Manual.

- PR interval, QRS duration, heart rate, RR, QT, QTc

The Fridericia QT correction formula (QTcF) calculated with the RR interval expressed in seconds should be used for clinical decisions.

Clinically significant abnormalities should be recorded on the relevant medical history/current medical conditions CRF page prior to informed consent signature and on the Adverse Events page thereafter. Clinically significant findings must be discussed with the Sponsor.

### **8.6.6      Pregnancy and assessments of fertility**

All pre-menopausal women who are not surgically sterile will have pregnancy testing. See the [Assessment Schedule](#) for timing of the protocol required pregnancy testing; additional pregnancy testing may be performed to meet local requirements. A positive urine pregnancy test requires immediate interruption of study treatment until serum  $\beta$ -hCG is performed and found to be negative.

If additional pregnancy testing is needed per local requirements, those additional results will be kept as source documentation only.

### **8.6.7      Immunogenicity (Anti-ACZ885 Antibodies)**

To assess potential immunogenicity, serum samples for determination of anti-ACZ885 antibodies (ADA) will be collected during the study (see [Assessment Schedule](#)).

Follow instructions outlined in the Central Laboratory Manual regarding sample collection, numbering, processing, and shipment.

In the case of an anaphylactic reaction occurring after injection, a sample will be taken at the time of the event and 8 weeks later. An immunogenicity positive subject at the end of the study will be followed up for three months.

### **Immunogenicity analytical method**

An ELISA based method will be used for the detection of potential ADA formation. The detailed method description to assess immunogenicity will be described in the bioanalytical raw data of the study and in the respective Bioanalytical Data Report (BDR).

#### **8.6.8 Local tolerability (subcutaneous injections)**

Local tolerability at the sites of s.c. injections will be evaluated by the investigator. Any local reactions should be observed until they have disappeared. An assessment of severity (i.e., none, mild, moderate, severe) of the following signs and symptoms: pain, redness, swelling, induration, hemorrhage and itch, and the exact location of any local reaction will be recorded in the eCRF.

### **8.7 Pharmacokinetics**

PK samples will be collected at the timepoints defined in the [Assessment Schedule](#) according to the instructions outlined in the Central Laboratory Manual regarding sample collection, numbering, processing and shipment. See [Section 8.9](#) regarding the potential use of residual samples.

In order to better define the PK profile, the timing of the PK sample collection may be altered based on emergent data. The number of samples/blood draws and total blood volume collected will not exceed those stated in the protocol.

Corporate Confidential Information

### **Pharmacokinetic parameters**

Concentrations will be expressed in mass per volume units. Missing values or those below the limit of quantification will be indicated in the data listings and treated as zero in data presentations and calculations.

For standard pharmacokinetic abbreviations and definitions see the list provided at the beginning of this protocol.

A previously utilized and validated mixed effects modeling approach may be used to characterize the exposure-related PK parameters (i.e., AUC and CL) of canakinumab. These results may be reported in a separate report from the final CACZ885X2205 clinical study report.

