### **1.3.2 Human pharmacokinetic data**

Canakinumab has the expected pharmacokinetics of an IgG1-type antibody with a low volume of distribution ( $V_{SS}=6.0$  L) and low clearance that is dependent on body weight (e.g.,  $CL=0.174$  L/day in a CAPS patient of body weight 70 kg, 0.11 L/day in a SJIA patient of body weight 33 kg and 0.23 L/day in a gout patient of body weight 93 kg). Half-lives vary between 21 and 30 days. Within the dose range studied, the pharmacokinetics of canakinumab were linear. The systemic exposure parameters, AUC and Cmax, increase in proportion to dose over the dose range of 0.30 to 10.0 mg/kg given as i.v. infusion and from 150 mg to 300 mg when administered as an s.c. injection. The absolute bioavailability of s.c. canakinumab is 70%. A mathematical model to characterize the binding kinetics of canakinumab to IL-1 $\beta$  has been created. The model successfully fits the patient data and allows estimation of canakinumab clearance and volumes of distribution, together with IL-1 $\beta$  rate of release and half-lives.

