Subjects who meet the eligibility criteria at screening will undergo evaluation of full baseline clinical and biomarker assessments prior to injection. Baseline assessments including safety laboratory evaluations and pulmonary function tests will not be available prior to dosing and for those measures eligibility criteria will be determined based on the screening results. Enrolled subjects will be randomized at a 1:1 ratio to receive treatment with either ACZ885 or placebo. On Days 1, 29, 57, 85, 113 and 141 patients will be administered s.c. dosing with ACZ885 at 300 mg or corresponding placebo treatment. All patients will return to the study center for safety and pharmacokinetic (PK) checks on an every four week basis at which time they will receive either study treatments depending on treatment arm. Additionally, patients will undergo clinical assessments that include pulmonary function tests with lung volumes, DLco, 6MWT, and clinical outcome assessments as outlined in the [Assessment Schedule](#).

At week 12, a second [F-18]FDG-PET/CT will be obtained. In addition, functional clinical measures Corporate Confidential Information will take place at this time point. The final dosing will take place on week 20, followed by a visit on week 24 Corporate Confidential Information

Corporate Confidential Information. Also included at the week 24 visit is the second HRCT assessment. Patients return for the end of study (EOS) visit at week 32.

A follow-up visit or phone call for SAEs must be performed 30 days following early discontinuation, or 8 weeks after last injection of study drug, whichever is later. If anaphylactic reactions occur after injection, two more immunogenicity samples (at the time of the event and 8 weeks later) need to be taken. Any patient who discontinues the study early will complete the Week 32, EOS visit. Patients discontinuing after week 12 will also undergo a second HRCT assessment at this visit, as assessed on a case-by-case basis by the Sponsor.

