## **4 Population**

This study will recruit patients with chronic active pulmonary sarcoidosis as defined by disease duration  $\geq 1$  year with evidence of persistent or progressive parenchymal changes as characterized by radiological evidence. A total of approximately 38 patients will be randomized to participate in the study. The sample size will be re-estimated at the interim analysis and number of randomized patients may be increased up to a maximum of 90.

The investigator must ensure that all subjects being considered for the study meet the following eligibility criteria.

Subject selection is to be established by checking through all inclusion/exclusion criteria at screening and first baseline prior to the first injection. Safety laboratory evaluations and pulmonary function tests taken at first baseline will not be available prior to first injection, and screening values should be used for inclusion in the study. A relevant record (e.g., checklist) of the eligibility criteria must be stored with the source documentation at the study site.

Deviation from any entry criterion excludes a subject from enrollment into the study.

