### **11.1 Analysis sets**

For all analysis sets, subjects will be analyzed according to the study treatment(s) received.

The safety analysis set will include all subjects that received any study drug.

The PK analysis set will include all subjects with available PK data and no protocol deviations with relevant impact on PK data.

The PD analysis set will include all subjects that received any study drug and that have no protocol deviations with relevant impact on PD data.

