#### **11.5.4 Pharmacokinetic/pharmacodynamic interactions**

The relationship between PK and efficacy/PD parameters may be investigated using graphical methods and simple regression models.

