### 5.2 Descriptive analyses

ACZ885 serum concentration data will be listed by subject and visit/sampling time point.

Corporate Confidential Information

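### The PK rule sets missing ACZ885 concentrations to zero along with results below quantification; for a missed post-dose sample in a treated patient that value is false

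*Protocol*

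**What the plan says.** Protocol Section 8.7, under Pharmacokinetic parameters, gives one rule for both kinds of absent number: "Missing values or those below the limit of quantification will be indicated in the data listings and treated as zero in data presentations and calculations". It makes no exception for post-dose samples in patients given ACZ885.

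The surrounding text that bears on it:

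- Sampling. Protocol 3.1: "All patients will return to the study center for safety and pharmacokinetic (PK) checks on an every four week basis". Section 8.7 adds that "the timing of the PK sample collection may be altered based on emergent data".
- Elimination. Protocol 1.3.2: "Half-lives vary between 21 and 30 days".
- Who is analysed. Protocol 11.1, repeated in SAP Section 4: "The PK analysis set will include all subjects with available PK data and no protocol deviations with relevant impact on PK data". The only PK exclusion in SAP Table 4-1 is lack of prior consent (INCL01).
- What is done with the data. SAP 5.1 names serum concentration as the only PK parameter. The visible sentence in SAP 5.2 is "ACZ885 serum concentration data will be listed by subject and visit/sampling time point"; the rest is redacted. Protocol 11.5.4: "The relationship between PK and efficacy/PD parameters may be investigated using graphical methods and simple regression models". An optional mixed-effects analysis of AUC and clearance is mentioned in 8.7.

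**The concern.** A result below quantification is a measurement: the sample was assayed and little or no drug was found. A missed, lost or unusable sample carries no information about the concentration. Coding it as zero asserts that a treated patient had no drug in serum.

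Three kinds of output could be affected. Per-visit arithmetic means would be too low and CVs too high, if the redacted text includes them. PK/PD plots and regressions would gain false zero-exposure points, which flatten an exposure-response slope. The AUC and clearance model would be affected only if zero-filled data were fed into it. Exposure-response matters somewhat here, because the dose rationale in Protocol 3.3 rests on reaching adequate circulating and tissue levels.

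Missing samples are foreseeable: Protocol 3.1 plans about 38 randomized and 30 completers. The rule does not say whether visits after withdrawal count as missing.

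**Working it through.** The plan states no figure that depends on this rule, so there is nothing to reproduce first. The check has two parts.

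**1. Is zero plausible after dosing?**

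Inputs: half-life t of 21-30 days, bioavailability 0.70 and volume 6.0 L (Protocol 1.3.2); 300 mg on Days 1, 29, 57, 85, 113 and 141 (Protocol 3.1); end-of-study visit on Day 224 (Protocol 8.1).

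Fraction of a dose remaining after d days = 2^(−d/t):

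| d | t = 21 | t = 30 |
|---|---|---|
| 28 (between PK checks) | 0.397 | 0.524 |
| 224 − 141 = 83 | 0.065 | 0.147 |

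For scale, take one compartment with instantaneous absorption. Each dose adds 0.70 × 300 / 6.0 = 35 mg/L, and doses are summed with the decay above.

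- Pre-dose trough after dose 1: 35 × 0.397 = 13.9 to 35 × 0.524 = 18.3 mg/L.
- Trough 28 days after dose 6: 22.9 to 37.7 mg/L.
- Day 224: 3.7 to 10.6 mg/L.

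These levels are rough, since the model ignores absorption and the inputs come from other indications. The assay's quantification limit is not visible. Even so, zero is not credible for a patient dosed as planned. In the same model, a patient who stopped after one dose would have only 0.02-0.2 mg/L at Day 224, where zero is nearly right.

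**2. What does zero-filling do?**

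Let m of n active-arm samples at a visit be missing at random, with q = m/n. The recorded value is the true concentration times an independent 0/1 indicator, which gives:

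- change in mean = −q
- reported CV = √[(1 + CV²)/(1 − q) − 1]
- slope on that concentration, relative to truth = CV²/(CV² + q)

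The slope factor assumes a linear active-arm regression on a single-visit concentration, with the response observed for the patient whose sample is missing.

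n = 19 is half of 38. n = 45 is half of the ceiling in Protocol Section 4, where the "number of randomized patients may be increased up to a maximum of 90". The documents give neither m nor the CV; both are assumed.

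Worked case, n = 19, m = 1, CV 0.40: q = 0.0526. The mean falls 5.3%; CV = √(1.16/0.9474 − 1) = 0.474; slope factor = 0.16/(0.16 + 0.0526) = 0.75.

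| n | m | Mean | Reported CV if true CV is 30 / 40 / 60% | Slope factor for the same CVs |
|---|---|---|---|---|
| 19 | 1 | −5.3% | 39 / 47 / 66% | 0.63 / 0.75 / 0.87 |
| 19 | 2 | −10.5% | 47 / 54 / 72% | 0.46 / 0.60 / 0.77 |
| 45 | 1 | −2.2% | 34 / 43 / 63% | 0.80 / 0.88 / 0.94 |
| 45 | 2 | −4.4% | 38 / 46 / 65% | 0.67 / 0.78 / 0.89 |

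A simulation (lognormal, CV 40%, 20,000 runs) gave median slope factors of 0.74 and 0.58 for n = 19 with m = 1 and 2, and 0.88 and 0.78 for n = 45. With one missed sample the median concentration moved on average only about −2.6% (n = 19) or −1.1% (n = 45).

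If visits after withdrawal count as missing and 4 of 19 are zero-filled (19 randomized, 15 completing), the mean falls 4/19 = 21.1% and a CV of 40% becomes about 68%.

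**The case against.** The strongest reply is that no visible output is shown to be harmed. The one concentration output left readable in the SAP is a listing, and listings flag missing values. Protocol 11.5.3, part of 8.7 and most of SAP 5.2 are redacted, and a handling rule could sit there. The PK/PD and mixed-effects analyses are optional, and no visible primary or secondary objective concerns PK. This stands, and it limits the severity. It does not rescue the protocol sentence: a different rule in the redacted SAP text would contradict it, and the SAP (Section 1.1) describes itself as implementing the protocol's analysis.

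The slope figures also need a condition. FVC is measured at the four-weekly visits through week 24 (SAP 6.1.1). If a whole visit is missed and the regression pairs same-visit data, the response is missing too and the pair drops out. The attenuation applies when only the PK sample is lost, or when concentration at one visit is paired with response at another. Including placebo patients, whose zeros are true, would also change the factor.

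Finally, no visible schedule row confirms PK sampling on Day 224. The argument does not need it; the 28-day figure is enough.

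**Conclusion.** The concern holds and is minor. As written, the rule assigns a false value to a missed post-dose sample in an ACZ885 patient, and nothing visible corrects it. With one missed sample and an assumed CV of 40%, the effect is 2-5% on a visit mean, a reported CV of 43-47%, and a slope factor of 0.75-0.88 under the condition above. Medians move less.

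Whether any reported summary is affected depends on redacted text and on optional analyses. Listings, samples before the first dose and placebo samples are not harmed. The primary FVC analysis and all visible decision rules are untouched.

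**What to change.** Replace the sentence in Protocol 8.7 with:

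> Concentrations below the limit of quantification will be treated as zero. Missing concentrations will be flagged in the listings, kept as missing, and left out of summaries, plots and calculations.

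Report the number of observed samples at each time point. Make SAP Section 5 say the same if its redacted text does not already do so. The cost is one protocol sentence and at most one in the SAP, with no new data and no change to the primary analysis.
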